27. Section 7.2.2: The following statement was added: “All subjects who sign an informed consent form, regardless of study procedures performed, will be assigned a screening number and have their data entered into the eCRF.”
28. Section 8.4.1:
- The statement, which referenced guidelines for ipilimumab, nivolumab, and pembrolizumab was deleted.
 - The title of the Medimmune Guideline for Toxicity Management for MEDI4736 was inserted.
29. Section 8.4.2: MEDI4736 dose modifications were updated according to the 19Aug2016 version of the AZ/Medimmune guidelines. Section 8.4.2.3 was changed as follows:
- Grade 3 was separated from Grade 2 modifications
 - Grade 3 modifications were added: "Hold MEDI4736. If AEs downgrade to \leq Grade 2 within 7 days or resolve to \leq Grade 1 or baseline within 14 days, resume MEDI4736 administration at next scheduled dose. Otherwise, discontinue MEDI4736 permanently.”
30. Section 8.4.3:
- For Point 2, “7 days or less” was changed to “ \leq half the planned dosing interval.”
 - For Point 3, “7 days” was changed to “half the planned dosing interval.”
31. Section 8.7: the following Note was added to the following assessments:
- Section 8.7.4: “NOTE: PER Amendment 2, samples will no longer be collected for analysis of TruCulture™, as the analyses were related to motolimod dosing. The collection time points for these assays have been removed from the flowchart in Section 3.2.”
 - Section 8.7.7: “NOTE: PER Amendment 2, samples will no longer be collected for analysis of HumanMap®. The collection time points for these assays have been removed from the flowchart in Section 3.2.”
 - Section 8.7.10: “NOTE: PER Amendment 2, samples will no longer be collected for analysis of MEDI4736 PK and immunogenicity for anti-drug antibodies (ADA), as sufficient samples have already been collected. The collection time points for these assays have been removed from the flowchart in Section 3.2.”
 - Section 8.7.11: “NOTE: PER Amendment 2, samples will no longer be collected for analysis of sPD-L1, as sufficient samples have already been collected. The collection time points for these assays have been removed from the flowchart in Section 3.2.”
 - Section 8.7.12: “NOTE: PER Amendment 2, samples will no longer be collected for analysis of circulating soluble factors, as sufficient samples have already been collected. The collection time points for these assays have been removed from the flowchart in Section 3.2.”
32. Sections 8.7.1, 8.7.3, 8.7.4, and 8.7.7: clarification was provided to indicate that collection of samples will be done according to the flowchart in Section 3.2.

CONFIDENTIAL

33. Section 8.7.6: the following clarification was added: "PBMCs will be assayed from 3 time points, which will be matched as closely as possible to the tumor biopsies (baseline, Cycle 2 Day 1 and the PBMC collection closest to disease progression)."
34. Section 8.7.8: The following statement was added: "An aliquot of the PBMC collection and/or tumor biopsy/archival tissue will be used for pharmacogenomics." The sentence "DNA will be isolated from whole blood" was deleted.
35. Sections 8.7.4, 8.7.5, 8.7.7, and 8.7.8: "shipped to" was changed to "analyzed by"
36. Administrative:
 - Spelling, grammar and typographical errors were corrected.
 - Formatting/administrative changes were implemented, as applicable.
 - Monitor and Study Monitor were standardized as "Clinical Monitor"
 - Study Physician was changed to Medical Monitor in Section 7.1.8

Amendment 3

Issue Date: 05-DEC -2016

Summary of Changes:

1. Synopsis: The following statement was added: "**Per Amendment 3**, optional MEDI4736 treatment extension beyond the initial 12-cycle treatment period (Core Study) will be available for subjects who complete the Core Study with Stable Disease or better; the optional treatment extension will be permitted for up to 12 additional cycles upon agreement with subject, Sponsor and Investigator. See Section 8.9 for details."
2. Section 3.1.12, Optional Study Treatment Extension: This section was changed **FROM:** "Treatment extension beyond 12 cycles is not planned" **TO:** "Optional MEDI4736 treatment extension beyond the initial 12-cycle treatment period (Core Study) will be available for subjects who complete the Core Study with Stable Disease or better; the optional treatment extension will be permitted for up to 12 additional cycles upon agreement with subject, Sponsor and Investigator. See Section 8.9 for details."
3. Section 3.1.15, Duration of Study: For Duration of Treatment, the following statement was added: "See Section 3.1.12 for optional treatment extension."
4. Section 3.1.16, On Study and Post Study Follow-up: The following statement was added: "See Section 3.1.12 for optional study treatment extension."
5. Section 3.1.16.1, End of Study Visit: The last sentence of paragraph 1 was clarified (changes in bold): "All subjects of childbearing potential who withdraw from study must have a serum pregnancy test done at the End of Study visit, **unless it was done within 7 days prior to the End of Study visit.**"
6. Section 3.2, Flowchart:
 - a. For last On Study Follow-up visit, changed from 91 to 90 days to allow consistency with protocol text.
 - b. Added Physical exam to On Study Follow-up visits
 - c. Added Concomitant meds collection to On Study Follow-up visits 2 and 3.
 - d. Added pregnancy test to last On Study Follow-up visit
7. Section 6.3.3, MEDI4736 Prep: The following sentence was updated based on feedback from Medimmune (changes in bold): "No incompatibilities between MEDI4736 and **polyethylene, polypropylene**, polyvinylchloride, or polyolefin copolymers have been observed."

CONFIDENTIAL

8. Section 6.3.3.1, MEDI4736 Prep for Cohort 0a: the following statement was added: **“Per Amendment 3, fixed dosing will be used for the optional study treatment extension as described in Section 3.1.12 and Section 8.9. See Section 6.3.3.2.”**
9. Section 6.3.3.2, MEDI4736 Prep for all other cohorts: The following statement was added: **“Per Amendment 3, fixed dosing will be used for all subjects who proceed with the optional study treatment extension as described in Section 3.1.12 and Section 8.9.”**
10. Section 6.3.4, MEDI4736 administration: The following changes were made based on feedback from Medimmune (changes in bold):
 - a. “Investigational product(s) must be administered at room temperature by controlled infusion ~~via an infusion pump~~ into a peripheral vein or central line.”
 - b. ~~“Since the compatibility of MEDI4736 with other IV medications and solutions, other than normal saline (0.9% [w/v] Sodium Chloride for Injection) or dextrose, is not known, the MEDI4736 solution should not be infused with through an IV line in which other solutions or medications. are being administered.”~~
 - c. “The total time between needle puncture of the MEDI4736 vial to start of administration should not exceed 4 hours at room temperature, or 24 hours at 2°C to 8°C (36°F to 46°F). **Standard infusion time is 60 ± 5 minutes. However, if there are interruptions during infusion (total infusion time not to exceed 4 hours), the total allowed time should not exceed 8 hours at room temperature. In the event that either preparation time or infusion time exceeds the time limits, a new dose must be prepared from new vials. If MEDI4736 administration has to be delayed, temporarily interrupted or the infusion rate decreased, or if administration time exceeds these limits, a new dose must be prepared from new vials.**”
 - d. Added “See Section 8.4.2.2 for management guidelines for infusion-related reactions.”
11. Section 6.4, Drug Requirements: Additional MEDI4736 requirements for optional study treatment extension were added.
12. Section 7.1.8, AESIs: additional details were added for AESIs to correspond with current Medimmune/AZ guidelines.
13. Section 8.4.2.2, Infusion-related reactions: The following clarification was added to Grades 1 and 2: “total infusion time not to exceed 4 hours”
14. Section 8.4.3, MEDI4736 Dose Modifications not due to Toxicities: The rules were clarified by changing **FROM:** 1)If the subject misses 2 consecutive planned doses, the subject should be discontinued from treatment. 2)If the dosing interruption is ≤ half the planned dosing interval, the originally planned drug administration should be given. Any respective protocol deviation should be documented, if applicable. 3)If the dosing interruption is greater than half the planned dosing interval, the dosing should be skipped and the next scheduled drug administration should be performed. The respective protocol deviation should be documented. **TO:**
 1. The originally planned visit/treatment schedule should be maintained in general, i.e., dosing interruptions should not reset the original treatment schedule. Exceptions may be made only for individual dosing days, whereby the interval between any two doses shall be no less than 21 days (for subjects on Q2W dosing, the interval shall be no less than 10 days). All resulting protocol deviations should be documented.

CONFIDENTIAL

2. If the dosing interruption causes 2 consecutive planned doses to be missed, the treatment should be discontinued.
 3. If the dosing interruption is \leq half the planned dosing interval, the originally planned dose should be given and the next dose(s) should be adjusted in accordance with #1, if necessary.
 4. If the dosing interruption is greater than half the planned dosing interval, the dose should be skipped and the next dose(s) should be adjusted in accordance with #1, if necessary.
15. Section 8.9 was added to provide additional details and flowchart for subjects who receive optional MEDI4736 treatment extension according to Section 3.1.12.
16. Administrative: Spelling, grammar and typographical errors were corrected; formatting changes were implemented, as applicable.

Amendment 4

Issue Date: 08-SEP-2017

Summary of Changes:

1. The duration of the treatment extension beyond the Core Study for MEDI4736 was changed from 12 cycles to “until confirmed disease progression.”
 - a. This change was implemented in the Synopsis and in Sections 3.1.12 and 8.9. Language was changed as follows (changes in bold): “Optional MEDI4736 treatment extension beyond the initial 12-cycle treatment period (Core Study) will be available for subjects who complete the Core Study with Stable Disease or better. The optional treatment extension will be permitted ~~for up to 12 additional cycles~~ upon agreement with subject, Sponsor and Investigator, **and it may continue until confirmed disease progression, unless there is unacceptable toxicity, withdrawal of consent, or another discontinuation criterion is met.** See Section 8.9 for details **regarding treatment extension and collection/reporting of adverse events during this period**”
 - b. The header and footnote 2 for the flowchart in Section 8.9.1 were also modified to reflect this change.
 - c. The following procedure point was added to Section 8.9: “AE/SAE collection and reporting will be performed according to the protocol requirements (Section 7.1) and until disease progression is documented. For AEs/SAEs that may be ongoing at the time of disease progression, follow-up will be performed until resolution or stabilization of the events or up to 90 days after the last dose of MEDI4736.”
2. Per current Medimmune recommendations, the language was updated for MEDI4736 dosing of subjects whose body weight drops to \leq 30 kg while on the study; in these cases, MEDI4736 dose will be weight based. Previously a fixed dose of 600 mg was recommended for \leq 30 kg. This change was made in the Synopsis and in Sections 2.1, 3.1.7, 6.3.3.2, and 8.9. The following clarification was added in Sections 6.3.3.2 and 8.9: “If a subject’s body weight drops to \leq 30 kg while on the study, the subject will receive weight-based dosing equivalent to 20 mg/kg of MEDI4736 as long as the body weight remains \leq 30 kg (e.g., a 30 kg subject would receive a 600 mg dose; a 25 kg subject would receive a 500 mg dose; etc.). When the weight improves to $>$ 30 kg, the subject may return to fixed dosing of MEDI4736 1500 mg.”
3. Section 5.2: the following change was made to exclusion criterion #17 (changes in bold): “Female subjects of childbearing potential who are sexually active with a nonsterilized male partner must use at least one highly effective method of contraception (see table below)

CONFIDENTIAL

from screening, and must agree to continue using such precautions for 90 days after the final dose of investigational product (MEDI4736).”

The following note was added: “**NOTE: For the standard of care, pegylated liposomal doxorubicin (PLD, Doxil®, Caelyx®), the package insert advises females of reproductive potential to use effective contraception during and for 6 months after last treatment with the drug. Therefore, all subjects of childbearing potential on this study should continue contraception use for 6 months after the last PLD administration.**”

4. Sections 6.3 (MEDI4736)- subsections for MEDI4736 information, preparation and administration were clarified and/or reorganized per current Medimmune recommendations and to maintain consistency with current protocols. The following statement was updated (changes in bold):
“The total time between needle puncture of the MEDI4736 vial to start of administration should not exceed 4 hours at room temperature, or 24 hours at 2°C to 8°C (36°F to 46°F). Standard infusion time is 60 ± 5 minutes. However, if there are interruptions during infusion (~~total infusion time not to exceed 4 hours~~), the total allowed **infusion** time should not exceed 8 hours ~~at room temperature~~. In the event that either preparation time or infusion time exceeds the time limits, a new dose must be prepared from new vials.”
5. Section 7.1.8 (AEIs): section was updated per current Medimmune recommendations. Diabetes insipidus and Type 1 diabetes mellitus were added to endocrine disorders. The following bullet was added:
 - **Other inflammatory responses** that are rare with a potential immune-mediated aetiology include, but are not limited to, myocarditis, pericarditis, and uveitis.
6. Section 8.4.2 (MEDI4736 Dose Modifications due to toxicities)
 - a. Added myocarditis to Pneumonitis/ILD bullet In Grades 1, 2, and 3 per current recommendations.
 - b. For Infusion-related reactions Grades 1 and 2, the phrase “total infusion time not to exceed 4 hours.” was deleted per current Medimmune guidelines.
7. Administrative: Spelling, grammar and typographical errors were corrected; formatting changes were implemented, as applicable.
8. US Study Chair’s affiliation was changed from University of Arizona College of Medicine at St Joseph’s Hospital to Arizona Oncology.

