3.1.8 Dosing Adjustments, Delays and Discontinuations

PER Amendment 2, motolimod dosing will be discontinued for all subjects.

Dose adjustment and management guidelines for toxicity related to the standard PLD regimen, motolimod, and MEDI4736 are outlined in Sections 8.2, 8.3, 8.4, respectively.

In the event of a delay in PLD dosing due to drug-related toxicity, doses of motolimod and MEDI4736 should also be delayed, so that the relative timing of the administration of each drug within each cycle is not altered. That is, the administration of PLD always constitutes cycle Day 1, and the dose dates of motolimod and MEDI4736 are determined relative to this date (see Section 3.1.7). Note that delays in the dosing of motolimod or MEDI4736 due to drug-related toxicity should not delay the 28-day dosing cycle of PLD, if possible. Likewise, any delay in MEDI4736 should not delay the administration of motolimod, and vice versa.

If PLD has to be discontinued due to PLD-related toxicities, the treatment with motolimod and/or MEDI4736 may continue, provided that the subject had received at least 2 doses of PLD (i.e., 2 cycles).

Irrespective of delay(s) in the dosing of the combination treatment, the disease assessments (CT, MRI) should not be delayed and must be conducted on the days originally scheduled, as calculated from the first study dose of PLD (Cycle 1 Day 1).

If a toxicity occurs that requires toxicity management in accordance with the toxicity management guidelines referenced above, and the toxicity causing drug can be clearly identified, then the respective guideline should be followed. If the toxicity causing drug cannot be identified, then the more conservative guideline should be followed.

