3.1.16 On Study and Post Study Follow-up

All subjects, whether they complete the study as planned, discontinue treatment prematurely, or withdraw from the study as per Section 3.1.10, will be followed as per institutional guidelines in accordance with the usual standard of care principles.

For all subjects who complete study treatment or discontinue treatment prematurely, there will be an On Study Follow-up Period (see Section 3.2) for 90 days after the last study drug administration, which will include collection of AE data (see Section 7.1.5 for details on collection of AEs).

If the determination is made to remove a subject from treatment at a visit that coincides with the first visit of the On Study Follow-up Period, any assessments required in the first On Study Follow-up visit that are not covered as part of the last on-treatment visit (usually correlative labs) should be done as soon as possible. If these assessments cannot be done on the same day, the subject should be brought back in at the earliest opportunity. Any assessments or correlative samples required by both the last on-treatment visit and the first On Study Follow-up visit should not be repeated.

Following the On Study Follow-up, there will be a Post Study Follow-up, where clinical outcomes data (dates of progression/relapse and survival) will be collected every 3 months for 3 years from initiation of treatment.

The Post Study Follow-up will include a query to determine if there were any immune-related adverse events (irAEs) during the 90 days since the last administration of study drug.

For subjects who do not continue Post Study Follow-up at one of the study sites after the end of study, the Principal Investigator, or the clinical team under the supervision of the Principal Investigator, will obtain this data through review of outside records or communication with the subject or his/her physician.

See Section 3.1.12 for optional study treatment extension.

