i - Standard of Care procedures may be used for eligibility assessments provided they meet the criteria specified in either the inclusion criteria or flowchart													

CONFIDENTIAL

Study Flowchart for All Subjects Except Dose Level 0a Cohort (Cont)	Treatment												On Study Follow-up			Post Study Follow-Up
	Cycle 7		Cycle 8		Cycle 9		Cycle 10		Cycle 11		Cycle 12		Last Study Drug Administration	Last Study Drug Administration	Last Study Drug Administration	
Cycle week	1		1		1		1		1		1		+28 ±3 days ^h	+56 ±7 days	+90 ±7 days End of Study	
Visit Day per Cycle	1±3	3±1	1±3	3±1	1±3	3±1	1±3	3±1	1±3	3±1	1±3	3±1				
Target Cumulative Visit Day	169	171	197	199	225	227	253	255	281	283	309	311				
Phase 1 & 2 STUDY DRUG ADMINISTRATION																
Pegylated liposomal doxorubicin - PLD (IV)	X		X		X		X		X		X					
MEDI4736 (IV)		X		X		X		X		X		X				
Tumor & Disease Assessments																
Disease Staging (date/stage at 1st diagnosis and at study entry)																
Disease Assessment by RECIST and irRECIST (including appropriate imaging)	X							X					+84 ± 7 days from last disease assessment			
Study Procedures & Examinations																
Eligibility Assessment and Informed Consent (IC) ⁱ																
Demographics (incl. DoB; sex; race; ethnicity)																
Medical history																
Physical Exam (incl. weight and ECOG Perf Status)	X		X		X		X		X		X		X	X	X	
Height																
Vital Signs (T, HR, BP, RR) ^b	X	X	X	X	X	X	X	X	X	X	X	X	X	X	X	
12-Lead ECG ^a	X		X		X		X		X		X		X		X	
Echocardiogram or MUGA						X							X			
Concomitant Medication / Procedure (name, indication, dose, route, start & end dates)	X	X	X	X	X	X	X	X	X	X	X	X	X	X	X	
Adverse Events (starting or worsening after IC) ^d	X	X	X	X	X	X	X	X	X	X	X	X	X	X	X	
Specimens for Laboratory Procedures																
Blood Hematology (complete blood count, differential, platelets) ^a	X	X	X	X	X	X	X	X	X	X	X	X	X	X	X	
Chemistry (gluc., BUN, crea., Na, K, Ca, Cl, CO2, PO4, Mg, prot., alb., Tbili., AST, ALT, ALP, LDH) ^a	X	X	X	X	X	X	X	X	X	X	X	X	X	X	X	
Chemistry cont. (Amylase and lipase) ^a	X	X	X	X	X	X	X	X	X	X	X	X	X	X	X	
Chemistry cont. (Free T3, Free T4, TSH) ^a	X		X		X		X		X		X		X	X	X	
Serum pregnancy test ^{a,f}	X				X				X				X		X	
CA-125 ^a	X		X		X		X		X		X		X			
Urine Pregnancy Test ^{a,f}																
Specimens for Correlative Assessments																
PBMC/Plasma Collection & Banking ^{a,g}	X												X		X	
MDSC (Seramatrix) ^{a,g} (US sites only)	X												X			

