4.1.1.1 Progression-free Survival Rate

The proportion of subjects who survive and do not progress - Progression Free Survival (PFS) rate- within the first 6 months of treatment based on RECIST v1.1 evaluated for the per-protocol analysis population constitutes the primary endpoint in Phase 2 of the study. PFS rate at 6 months will be based on disease assessments at the scheduled visit at the start of Cycle 7.

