- In the Study Flowchart for non-Cohort 0a Subjects, On Study Follow-up Intervals were changed from +14 to +28 days and from +42 to +56 days to align with the Q4W dosing intervals of the study.
 - MDSC: it was clarified that MDSC will be collected at US sites only (logistical reasons).
 - Disease assessment during On Study Follow-up was changed from a specific study visit to “+84 ± 7 days from last disease assessment.” This allows the frequency of disease assessments to remain constant for subjects who complete the study as well as those who discontinue early.
13. Section 4.1.1.1: the following sentence was added: “PFS rate at 6 months will be based on disease assessments at the scheduled visit at the start of Cycle 7.”
14. Section 4.2.2: The following was changed **FROM:** “The Per-Protocol (PP) Population for safety and tolerability is defined as all subjects who received at least 75% of the scheduled doses of MEDI4736, motolimod, and PLD over the first **2 cycles**, as well as respective safety assessments, without major protocol violations over the entire DLT Evaluation Period (as defined in Section 3.1.9). The Intent-To-Treat (ITT) Population for safety and tolerability is defined as all subjects who receive at least one dose of PLD, motolimod or MEDI4736. In Phase 1, for the primary endpoint of determining DLTs and the MTD, the analysis of safety and tolerability will be based on the PP Population. In both Phases 1 and 2, the overall analysis of safety and tolerability will be based on the ITT Population.” **TO:** “The Per-Protocol (PP) Population for DLT Assessment includes:
- All subjects who experience a DLT at any time during the DLT Evaluation Period (as defined in Section 3.1.9)
 - All subjects with no DLT who receive at least 75% of the scheduled doses of MEDI4736, motolimod, and PLD as well as respective safety assessments, without major protocol violations, over the entire DLT Evaluation Period (as defined in Section 3.1.9).
- Refer to Section 3.1.11 for subject replacements. The Intent-To-Treat (ITT) Population for safety and tolerability is defined as all subjects who receive at least one dose of PLD, motolimod or MEDI4736. In Phase 1, for the primary endpoint of determining DLTs and the MTD, the analysis of safety and tolerability will be based on the PP Population for DLT Assessment. In both Phases 1 and 2, the overall analysis of safety and tolerability will be based on the ITT Population for safety and tolerability.

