8.5.3.4 Duration of Response

Duration of overall response: The duration of overall response is measured from the time measurement criteria are met for CR or PR (whichever is first recorded) until the first date that recurrent or progressive disease is objectively documented (taking as reference for progressive disease the smallest measurements recorded since the treatment started).

The duration of overall CR is measured from the time measurement criteria are first met for CR until the first date that progressive disease is objectively documented.

Duration of stable disease: Stable disease is measured from the start of the treatment until the criteria for progression are met, taking as reference the smallest measurements recorded since the treatment started, including the baseline measurements.

8.6 irRECIST Guidelines

Determination of response via irRECIST should take into consideration all target and non-target lesions.

A key distinction between standard RECIST 1.1 criteria and immune-related response criteria is that irRECIST requires early evidence of progressive disease (i.e., a determination of irPD \leq 12 weeks after starting study treatment) be confirmed by repeat, consecutive imaging \geq 4 weeks after the initial documentation in the absence of rapid clinical deterioration. During this interim \geq 4 week period, subjects should continue to be followed per protocol, including continued dosing of the study drug(s).

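### Off-treatment scans are timed from the last scan rather than from Cycle 1 Day 1, so an off-schedule scan after a stop in Cycles 4–6 can displace the Day 169 scan

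*Protocol*

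**What the plan says.** **On treatment.** Protocol Section 3.1.8 says that, despite dosing delays, disease assessments "must be conducted on the days originally scheduled, as calculated from the first study dose of PLD (Cycle 1 Day 1". The flowcharts in Section 3.2 place them at Days 85, 169 and 253 on the line "Target Cumulative Visit Day" (day 1 of Cycles 4, 7 and 10).

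**After treatment.** In the On Study Follow-up columns of both core flowcharts, and in SAP Table 1, the next assessment is due "84 ± 7 days from last disease assessment". Section 8.1 (Amendment 2) gives the purpose: "This allows the frequency of disease assessments to remain constant for subjects who complete the study as well as those who discontinue early". The log and the current flowcharts use the same wording, so the rule is in force.

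**Length of follow-up.** Section 3.1.16 sets an "On Study Follow-up Period (see Section 3.2) for 90 days after the last study drug administration", and the last flowchart visit is at "90 ±7 days End of Study". After that, only dates of progression and survival are collected.

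**Endpoint.** Section 4.1.1.1 states that "PFS rate at 6 months will be based on disease assessments at the scheduled visit at the start of Cycle 7". SAP Section 3.8.1 also defines 6 months as that visit. It tests the rate with a Kaplan-Meier confidence interval and lets clinical progression or death count as events.

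**The concern.** The plan runs two clocks. During treatment the scan calendar is fixed. After treatment it restarts at whatever assessment came last, and nothing restricts that to a scheduled one. A single off-schedule scan between Day 85 and Day 169 therefore moves the next required scan, possibly past the visit that defines the primary endpoint.

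For a subject who is still progression-free, two errors become possible:

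- A progression before Day 169 is first seen at a later scan, is dated after 6 months, and counts as progression-free.
- No later scan falls within follow-up, and the subject is censored at the extra scan.

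Both depend on having stopped treatment and on someone ordering an extra scan, so the resulting censoring may be informative.

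**Working it through.** **1. The plan's own figure.** Inputs from Protocol Section 3.1.6: null rate 0.25, alternative 0.45, one-sided exact test at 0.05, 41 evaluable subjects, 80% power. Rejection needs at least 16 of 41 progression-free: P(X ≥ 16 | 41, 0.25) = 3.33% and P(X ≥ 16 | 41, 0.45) = 82.3%. Forty-one is the smallest size at which power is at least 80% for it and for every larger size checked (up to 199). The sample size reproduces.

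**2. No extra scan.** Day 85 + 84 = Day 169, window 162–176. The two rules coincide.

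**3. Extra scan on Day X.** The next scan is due X + 84, window X + 77 to X + 91. It can still fall within 162–176 if X + 77 ≤ 176, that is X ≤ 99. A scan on Day 162 or later lies inside the Day 169 window itself. So the Day 169 scan is lost for X = 100 to 161, with the next scan on Day 177 or later (100 + 77). If the 4-week minimum in Section 4.1.1 is applied, X is at least 85 + 28 = 113.

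**4. Is there any further protocol scan?** Let L be the day of the last dose. Follow-up ends at L + 90, window L + 83 to L + 97.

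- On target days, a scan fits if X + 84 ≤ L + 90, that is X − L ≤ 6.
- With both windows fully used, it fits if X + 77 ≤ L + 97, that is X − L ≤ 20.

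Beyond 20 days, none fits. Two examples with last dose on Day 115, where follow-up ends Day 205 (198–212):

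- Extra scan Day 141, 26 days after the dose: next scan Day 225 (218–232). None fits.
- Extra scan Day 120: next scan Day 204 (197–211). It fits, but 35 days after Day 169.

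**5. Which stops are affected?** On the every-4-weeks schedule used in Phase 2:

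| Last dose (Day 3 of cycle) | Follow-up ends, target | Latest | Day 169 inside? |
|---|---|---|---|
| Day 59 (Cycle 3) | 149 | 156 | no |
| Day 87 (Cycle 4) | 177 | 184 | yes |
| Day 115 (Cycle 5) | 205 | 212 | yes |
| Day 143 (Cycle 6) | 233 | 240 | yes |

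**6. Chance that something is missed, per affected subject.** Assume a constant hazard h = −ln(p)/168, with p the rate at Day 169. The chance of progressing between X and Day 169 is 1 − exp(−h(169 − X)). For p from 0.45 to 0.25 this is 23% to 37% at X = 113, and 12% to 21% at X = 141.

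**7. Illustrative effect on the 16-of-41 rule.** The number k of affected subjects is assumed, because the documents give no rate of early stopping or of extra scans. If all k are scored progression-free, type I error is P(X ≥ 16 − k | 41 − k, 0.25): 3.3% for k = 0, 5.4% for k = 1, 8.6% for k = 2. If all k are scored as progressed, power is P(X ≥ 16 | 41 − k, 0.45): 82.3%, 78.6% and 74.4%.

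**The case against.** The best defence is that the schedule as drawn is consistent. No flowchart has a scan at stopping, and Section 7.2.6 asks for a complete final evaluation without naming imaging. The amendment's stated aim is constant frequency, which suggests that the last scheduled scan was meant. This stands in part: the harm is conditional on an extra scan and on the literal reading. But the text permits that reading, and the 4-week minimum in Section 4.1.1 would be redundant if scans were always 84 days apart.

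Several stronger conclusions are tempting and are not supported:

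- *Anyone who stops early loses the Day 169 scan.* Without an extra scan, a stop in Cycles 4–6 keeps it.
- *The irRECIST repeat scan will trigger the problem.* Section 8.6 wants early progression to "be confirmed by repeat, consecutive imaging", but only for progression within 12 weeks and with dosing continuing, so the fixed calendar applies. Such a subject will almost always already be a RECIST 1.1 event.
- *Any scan for suspected progression does harm.* It matters only if negative. A subject who starts other therapy leaves the study at once (Section 3.1.10), and re-anchoring recovers nothing there.
- *A scan two weeks after the last dose leaves no further scan.* That is true on target days only. For last dose Day 115 and scan Day 129, the windows 206–220 and 198–212 overlap.
- *One misdated subject gives a 6.7% type I error.* That is P(X ≥ 15 | 41, 0.25), which presumes that the affected subject would always truly have progressed. Fixing one subject as progression-free gives 5.4%.

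The SAP also softens the effect. Clinical progression or death can stand in for a missing scan (Section 3.3.1), and progression dates are sought every 3 months, including from outside records (Protocol Section 3.1.16). Silent radiological progression is not reliably recovered in this way. The SAP's binomial sensitivity analysis appears to count subjects who discontinued treatment as progressed, so they could not be scored progression-free there.

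**Conclusion.** The point holds conditionally. It needs a subject who stops in Cycles 4–6 without progression or new therapy, a negative off-schedule scan on Days 100–161, and the literal reading of the follow-up rule. The scan supporting the primary endpoint is then displaced to Day 177 or later. If the extra scan came more than 20 days after the last dose, no protocol scan follows at all.

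The number of such subjects cannot be derived from the documents. The shift from 3.3% to 5.4% for one subject shows sensitivity. It does not estimate the error rate of the Kaplan-Meier test that the SAP makes primary. The change is worth making because it is cheap and protects the decisive assessment.

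Stops in Cycles 1–3 are a different matter: the 90-day limit ends follow-up by Day 156, so Day 169 is missed whichever clock is used.

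**What to change.** In both core flowcharts and in SAP Table 1, replace the follow-up rule with: every 84 ± 7 days on the calendar counted from Cycle 1 Day 1 (Days 85, 169, 253, 337), regardless of any unscheduled assessment. Extend the scan-timing sentence in Section 3.1.8 to subjects who have stopped treatment and are in On Study Follow-up. State how this fits with the 4-week minimum in Section 4.1.1, since an extra scan on Days 142–161 would be followed by the Day 169 scan in less than 28 days.

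The cost is wording only, with no added planned scan. The downside is that a few subjects would be scanned again sooner than 84 days after an extra scan.

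This covers stops in Cycles 4–6. For stops in Cycles 1–3, the plan needs a separate statement of how Day 169 status is obtained once follow-up has ended.
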